7.10.8. Serum for Exploratory Analysis

Blood samples (10 mL) to provide approximately 3 mL serum will be collected into appropriately labeled tubes according to the times outlined in the [Schedule of Activities](#). These samples may be used for the evaluation of exploratory biomarkers that may include markers related to atopic dermatitis and/or other inflammatory conditions and/or the mechanism of action of PF-04965842. These samples are for biomarker analysis and will not be used for genetic testing.

Detailed processing, storage and shipment instructions will be provided in the lab manual.

7.10.9. Cell-free Plasma for Exploratory Analysis

Blood samples (10 mL) will be collected into appropriately labeled tubes according to the times outlined in the [Schedule of Activities](#). These samples may be used for the evaluation of exploratory biomarkers from cell-free plasma that may include markers related to atopic dermatitis and/or other inflammatory conditions and/or the mechanism of action of PF-04965842. These samples are for biomarker analysis and will not be used for genetic testing.

Detailed processing, storage and shipment instructions will be provided in the lab manual.

7.10.10. Gene Expression Analysis

Blood samples (2.5 mL) for the assessment of gene expression (mRNA analysis) will be collected in appropriately labeled PAXgene Blood RNA Tubes. Samples will be collected according to the times outlined in the [Schedule of Activities](#). These samples may be used for the evaluation of exploratory biomarkers that may include markers related to atopic dermatitis and/or other inflammatory conditions and/or the mechanism of action of PF-04965842. These samples are for biomarker analysis and will not be used for genetic testing.

Detailed Processing, Storage and Shipment Instructions will be provided in the Lab Manual.

7.10.11. Shipment of Pharmacodynamic Samples

The shipment address and assay lab contact information will be provided to the investigator site prior to initiation of the study.

8. ADVERSE EVENT REPORTING

8.1. Adverse Events

All observed or volunteered AEs regardless of treatment group or suspected causal relationship to the investigational product(s) will be reported as described in the following sections.

For all AEs, the investigator must pursue and obtain information adequate both to determine the outcome of the AE and to assess whether it meets the criteria for classification as a serious adverse event (SAE) requiring immediate notification to Pfizer or its designated

representative. For all AEs, sufficient information should be obtained by the investigator to determine the causality of the AE. The investigator is required to assess causality. Follow-up by the investigator may be required until the event or its sequelae resolve or stabilize at a level acceptable to the investigator, and Pfizer concurs with that assessment.

As part of ongoing safety reviews conducted by the sponsor, any nonserious AE that is determined by the sponsor to be serious will be reported by the sponsor as an SAE. To assist in the determination of case seriousness, further information may be requested from the investigator to provide clarity and understanding of the event in the context of the clinical study.

8.2. Reporting Period

For SAEs, the active reporting period to Pfizer or its designated representative begins from the time that the subject provides informed consent, which is obtained prior to the subject's participation in the study, ie, prior to undergoing any study-related procedure and/or receiving investigational product, through and including 28 calendar days after the last administration of the investigational product. SAEs occurring to a subject after the active reporting period has ended should be reported to the sponsor if the investigator becomes aware of them; at a minimum, all SAEs that the investigator believes have at least a reasonable possibility of being related to investigational product are to be reported to the sponsor.

AEs (serious and non-serious) should be recorded on the case report form (CRF) from the time the subject has taken at least 1 dose of investigational product through the subject's last visit.

8.3. Definition of an Adverse Event

An AE is any untoward medical occurrence in a clinical investigation subject administered a product or medical device; the event need not necessarily have a causal relationship with the treatment or usage. Examples of AEs include but are not limited to:

- Abnormal test findings;
- Clinically significant symptoms and signs;
- Changes in physical examination findings;
- Hypersensitivity;
- Progression/worsening of underlying disease;
- Drug abuse;
- Drug dependency.

Additionally, they may include the signs or symptoms resulting from:

- Drug overdose;
- Drug withdrawal;
- Drug misuse;
- Drug interactions;
- Extravasation;
- Exposure during pregnancy (EDP);
- Exposure via breastfeeding;
- Medication error;
- Occupational exposure.

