2.4.2.2. Safety Endpoints

- Incidence of treatment-emergent adverse events.
- Incidence of specific clinical laboratory abnormalities (anemia, neutropenia, thrombocytopenia, lymphopenia, lipid profile, liver function tests [LFTs]).

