5.8.2. Prohibited Medications and Treatments

Subjects are required to discontinue and avoid using certain medications and treatments (see [Inclusion/Exclusion Criteria](#) and [Appendix 3](#)). Subjects should be instructed at each visit to contact the study site investigator promptly if there are any intended changes or additions to concomitant medications.

All medications and treatments that could affect atopic dermatitis must be discontinued except oral antihistamines. Due to the potential to affect atopic dermatitis with ultraviolet light exposure, subjects must also avoid prolonged exposure to the sun and avoid the use of tanning booths, sun lamps or other ultraviolet light sources during the study.

For the purposes of this protocol, dietary supplements are defined as vitamins, minerals, purified food substances, and herbals with pharmaceutical properties. Vitamins, minerals and purified food substances are allowed in amounts not known to be associated with adverse effects (such as hypervitaminosis).

Herbals supplements are only allowed on a case by case basis; please contact the Pfizer staff. Herbal medications with unknown properties or known beneficial effects for AD or that are known to have an effect on drug metabolism (eg St. John's Wort) must be discontinued at least 1 week or 5 half-lives (whichever is longer) before the first dose of investigational product.

Restrictions on certain vaccinations are described in [Section 5.8.3](#).

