8.12. Withdrawal Due to Adverse Events (See Also the Section on [Subject Withdrawal](#))

Withdrawal due to AEs should be distinguished from withdrawal due to other causes, according to the definition of AE noted earlier, and recorded on the appropriate AE CRF page.

When a subject withdraws because of an SAE, the SAE must be reported in accordance with the reporting requirements defined below.

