9.3. Safety Analysis

All subjects who receive investigational product (safety population) will be included in the safety analyses. All the safety data will be summarized descriptively through appropriate data tabulations, descriptive statistics, categorical summaries, and graphical presentations. Safety endpoints for the study include:

- On-treatment AEs and SAEs.
- Withdrawals from active treatment due to AEs.
- Serious infections, defined as any infection (viral, bacterial, and fungal) requiring hospitalization or parenteral antimicrobials.
- Safety laboratory tests (eg, anemia, neutropenia, thrombocytopenia, lymphopenia, lipid profile, LFTs).
- Vital signs.

- ECG parameters if applicable.

Safety data will be reviewed and summarized on an ongoing basis during the study to evaluate the safety of subjects. A set of safety summary tables by treatment will be produced to evaluate any potential risk associated with the safety and toleration of administering the investigational product, continuous outcomes (eg, blood pressure, heart rate etc.) will be summarized using N, Mean, Median, Standard Deviation etc. Categorical outcomes (eg, occurrence of any adverse event) will be summarized by subject counts and percentage. Change from baseline on laboratory data and vital signs will be additionally summarized. Subject listings will also be produced for these safety endpoints. The safety endpoints will be listed and summarized in accordance with Pfizer Data Standards. The safety analyses will be carried out in the safety population, detailed analyses will be described in the SAP.

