5.2. Safety Analysis Set

The safety analysis set (SAS) will be all subjects who receive at least 1 dose of investigational product. The safety analysis set will include the follow-up period. The safety analysis set excluding follow-up period data may be conducted as a sensitivity analysis.

The final safety database will include all reported safety data at the time of database release.

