8.2.3. Statistical Analyses for Safety

The analysis population for safety is described in Section 5.2. Safety and tolerability will be assessed by clinical review of all relevant parameters including adverse experiences (AEs) and laboratory tests. A complete list of laboratory parameters can be obtained in Section 7.3 of the protocol.

All the tables, listings and graphs for adverse events, lab parameters and vital sign will follow Pfizer standards.

A 3-tier approach will be used to summarize AEs. Under this approach, AEs are classified into 1 of 3 tiers.

Tier-1 events: These are pre-specified events of clinical importance and are maintained in a list in the product's Safety Review Plan.

Tier-2 events: These are events that are not tier-1 but are "common". A MedDRA Preferred Term (PT) is defined as a tier-2 event if there are at least 4 in any treatment group.

Tier-3 events: These are events that are neither tier-1 nor tier-2 events.

There will be no adjustment for multiple comparisons or stratification factors in the analyses unless specified. For tier-1 and tier-2 events, the proportion of AEs observed in each treatment groups will be presented along with the point estimates and associated 90% confidence intervals of the risk difference for each active treatment compared with placebo. The exact methods (Chan and Zhang, 1999) and asymptotic approach will be employed for analysis of tier-1 and tier-2 events. For tier-1 events p-values may be included in the presentations. AEs will be arranged in the output sorted in descending point estimate of the risk difference within system organ class. Footnotes in the outputs will include the methods used to derive any p-values and confidence intervals as per Pfizer standards. The exposure adjusted summaries for the Tier 1 and Tier 2 events will also be conducted.

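### Disease worsening counts as an adverse event, so the any-TEAE and especially the AE-withdrawal comparisons mix lack of efficacy with harm and could mask an excess on effective doses

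*Protocol*

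**What the plan says.** - Protocol 8.3 gives "Progression/worsening of underlying disease" as an example of an adverse event. Neither document exempts AD, the disease under study.
- Protocol 8.12: "Withdrawal due to AEs should be distinguished from withdrawal due to other causes, according to the definition of AE noted earlier". A subject who stops because AD worsened can therefore be counted as an AE withdrawal.
- Both totals are safety endpoints: "Incidence of treatment-emergent adverse events" (Protocol 2.4.2.2) and "Withdrawals from active treatment due to AEs" (Protocol 9.3).
- Protocol 5.8.2, for every arm including placebo: "All medications and treatments that could affect atopic dermatitis must be discontinued except oral antihistamines".
- SAP 8.2.3 compares AEs term by term. "A MedDRA Preferred Term (PT) is defined as a tier-2 event if there are at least 4 in any treatment group", and tier-1 and tier-2 events are shown with "associated 90% confidence intervals of the risk difference for each active treatment compared with placebo".
- SAP 5.2: "The safety analysis set will include the follow-up period". Leaving that period out is only an optional sensitivity analysis, although Protocol 9.3 speaks of on-treatment AEs.
- Neither document plans an any-TEAE or AE-withdrawal summary without the AD-worsening terms.

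**The concern.** Recording disease worsening as an AE is not an error. The gap is in the analysis. With other AD treatment stopped, on-treatment worsening is plausibly most frequent on placebo and on weak doses, and it is what an effective dose should prevent. A dose that works removes some of these events from its own arm. It can then carry more toxicity of other kinds before its pooled AE or AE-withdrawal rate rises above placebo.

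This is a four-dose study whose safety results are meant to support further development. If tolerability across doses is read from pooled totals, the safety side of the dose-response is partly an inverted copy of the efficacy side.

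**Working it through.** **Inputs.** About 50 subjects per arm (250/5, Protocol 9.1). Tier-2 threshold of 4 in a group (SAP 8.2.3), read as subjects: 4/50 = 8%. The documents give no rate for any AE, AE withdrawal or AD worsening, so there is no figure of the plan's own to reproduce. Every rate below is an assumption.

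**1. AE withdrawals.** A subject stops treatment once, so the causes add: total = other AEs + AD worsening. Assume withdrawals for other AEs of 4% on placebo (2 of 50) and 10% on drug (5 of 50), a true excess of 6 points.

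| AD-worsening withdrawals, placebo vs drug | Total placebo | Total drug | Apparent difference |
|---|---|---|---|
| 2% vs 2% | 6% | 12% | +6 |
| 6% vs 2% | 10% | 12% | +2 |
| 8% vs 2% | 12% | 12% | 0 |
| 12% vs 2% | 16% | 12% | -4 |

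In the third row AD worsening accounts for 4 of 50 on placebo and 1 of 50 on drug. A net three subjects cancel the excess.

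**2. Any TEAE.** Let h be the risk of any AE other than AD worsening and w the risk of an AD-worsening AE, taken as independent. Then P(any AE) = 1 - (1 - h)(1 - w). Take h = 50% on placebo and 60% on drug, a true excess of 10 points.

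- w = 5% in both arms: 1 - 0.50×0.95 = 52.5% and 1 - 0.40×0.95 = 62.0%, so +9.5 points.
- w = 20% placebo, 5% drug: 1 - 0.50×0.80 = 60.0% and 62.0%, so +2.0 points.
- w = 5% placebo, 15% drug (for example, flares after stopping an effective dose): 52.5% and 1 - 0.40×0.85 = 66.0%, so +13.5 points. The bias is then against the drug.

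**3. Placebo worsening needed to cancel a 10-point excess.** Setting the two totals equal gives w0 = 1 - (1 - h0 - 0.10)(1 - w1)/(1 - h0), where 0 is placebo and 1 is drug.

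| Other AEs on placebo (h0) | w0 if w1 = 0 | w0 if w1 = 5% |
|---|---|---|
| 30% | 14.3% | 18.6% |
| 40% | 16.7% | 20.8% |
| 50% | 20.0% | 24.0% |
| 60% | 25.0% | 28.75% |

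That is about 7 to 14 of 50 placebo subjects, above the tier-2 threshold. If these events code to one preferred term, that term has its own row and confidence interval.

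**4. Below the threshold.** With at most 3 of 50 (6%) on placebo and none on drug, the any-AE difference moves by at most 0.06×(1 - h0): 4.2, 3.0 and 2.4 points at h0 = 30%, 50% and 60%.

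**5. Precision.** The 90% half-width is 1.645×√[(p0(1 - p0) + p1(1 - p1))/50]. It is 16.0 points at 60% vs 62%, 10.7 points at 12% vs 12%, and 8.3 points at 4% vs 10%.

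**The case against.** The strongest reply is that the term-level table already does the work. By steps 3 and 4, AD worsening frequent enough to cancel a 10-point any-TEAE excess would have its own row, and below the threshold the shift is small. This stands for any TEAE. It does not carry over to withdrawals: the tier rule applies to AE terms, not to reasons for stopping. In the illustration the 4 placebo events would earn an AE row, but that row would not show that they led to withdrawal.

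Second, SAP 8.2.1 presents reasons for withdrawal, and Protocol 9.3 calls for subject listings. The SAP summary concerns leaving the study, whereas the endpoint is stopping active treatment, and Protocol 6.4 keeps subjects who stop treatment in the study. A reason coded as AE would not reveal AD worsening. Listings allow the split to be recovered, but only after the fact.

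Third, safety is summarised descriptively and no decision rule uses these totals. At about 50 per arm the shifts lie within the half-widths in step 5, and even the undiluted 6-point withdrawal excess would not exclude zero. This limits the weight of the point. It does not make the mixed total easier to interpret.

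Fourth, the premise is softened by washout. Topical treatments stop 1 week and oral immunosuppressants 4 weeks before the first dose (Protocol 4.2), and AEs enter the case report form only after that dose (8.2), so some worsening precedes recording. Overlap of the two event types within subjects would shrink the any-AE effect, to nothing if complete. Both stand.

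Fifth, serious infections, laboratory abnormalities, vital signs and ECG are separate and are not driven by AD worsening. The Safety Review Plan and the sponsor's table standards were not available and may already deal with it.

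**Conclusion.** The pooled any-TEAE and AE-withdrawal comparisons mix lack of efficacy with harm when the plan is followed as written. They could mask or shrink a true excess on effective doses if on-treatment AD worsening is more frequent on placebo. The AE-withdrawal comparison is the more fragile: on the assumed rates, a net three of about 50 subjects turn a 6-point excess into no difference. For any TEAE, full cancellation of a 10-point excess needs about 14% to 29% worsening on placebo, which would be visible at term level.

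A reader might go further and infer that placebo failures do hide a real excess of harm. The documents do not support that. They contain no rates, and masking needs both a true excess on drug and clearly more AD worsening on placebo. Nor is the direction fixed in the drug's favour, because the safety set includes the off-drug follow-up, where flares after an effective dose would count against the drug arms. That offset applies to the AE count; withdrawal from active treatment is an on-treatment event. A reader might also extend the point to severe-AE counts, but neither Protocol 2.4.2.2 nor 9.3 names these as an endpoint.

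This is a cheap, worthwhile improvement to the plan rather than a flaw that undermines its safety analysis.

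**What to change.** Keep collecting AD worsening as an AE. In SAP 8.2.3 and Protocol 9.3:

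- fix, before unblinding, the list of preferred terms that count as AD worsening;
- present on-treatment any-TEAE and AE withdrawal from treatment by arm, each with and without those terms;
- give withdrawals for AD worsening their own row;
- show follow-up events separately from on-treatment events.

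The cost is SAP and protocol wording, a short term list and a few extra summary lines. No new data are needed and subject management does not change. The downside is that a flare with another cause may drop out of the restricted line; the all-inclusive line beside it still shows that event.

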8.4. Medication Errors

Medication errors may result, in this study, from the administration or consumption of the wrong product, by the wrong subject, at the wrong time, or at the wrong dosage strength. Such medication errors occurring to a study participant are to be captured on the medication error CRF, which is a specific version of the AE page, and on the SAE form when appropriate. In the event of medication dosing error, the sponsor should be notified immediately.

Medication errors are reportable irrespective of the presence of an associated AE/SAE, including:

- Medication errors involving subject exposure to the investigational product;
- Potential medication errors or uses outside of what is foreseen in the protocol that do or do not involve the participating subject.

Whether or not the medication error is accompanied by an AE, as determined by the investigator, the medication error is captured on the medication error version of the AE page and, if applicable, any associated AE(s) are captured on an AE CRF page.

8.5. Abnormal Test Findings

The criteria for determining whether an abnormal objective test finding should be reported as an AE are as follows:

- Test result is associated with accompanying symptoms; and/or

- Test result requires additional diagnostic testing or medical/surgical intervention; and/or
- Test result leads to a change in study dosing or discontinuation from the study, significant additional concomitant drug treatment, or other therapy; and/or
- Test result is considered to be an AE by the investigator or sponsor.

Merely repeating an abnormal test, in the absence of any of the above conditions, does not constitute an AE. Any abnormal test result that is determined to be an error does not require reporting as an AE.

8.6. Serious Adverse Events

A serious adverse event is any untoward medical occurrence at any dose that:

- Results in death;
- Is life-threatening (immediate risk of death);
- Requires inpatient hospitalization or prolongation of existing hospitalization;
- Results in persistent or significant disability/incapacity (substantial disruption of the ability to conduct normal life functions);
- Results in congenital anomaly/birth defect.

Medical and scientific judgment is exercised in determining whether an event is an important medical event. An important medical event may not be immediately life-threatening and/or result in death or hospitalization. However, if it is determined that the event may jeopardize the subject or may require intervention to prevent one of the other AE outcomes, the important medical event should be reported as serious.

Examples of such events are intensive treatment in an emergency room or at home for allergic bronchospasm; blood dyscrasias or convulsions that do not result in hospitalization; or development of drug dependency or drug abuse.

8.6.1. Protocol-Specified Serious Adverse Events

There are no protocol-specified SAEs in this study. All SAEs will be reported by the investigator as described in previous sections, and will be handled as SAEs in the safety database (see the section on [Serious Adverse Event Reporting Requirements](#)).

8.6.2. Potential Cases of Drug-Induced Liver Injury

Abnormal values in AST and/or ALT levels concurrent with abnormal elevations in total bilirubin level that meet the criteria outlined below in the absence of other causes of liver injury are considered potential cases of drug-induced liver injury (potential Hy's law cases) and should always be considered important medical events.

The threshold of laboratory abnormalities for a potential case of drug-induced liver injury depends on the subject's individual baseline values and underlying conditions. Subjects who present with the following laboratory abnormalities should be evaluated further to definitively determine the etiology of the abnormal laboratory values:

- Subjects with AST or ALT and total bilirubin baseline values within the normal range who subsequently present with AST or ALT values ≥ 3 times the ULN concurrent with a total bilirubin value $\geq 2 \times$ ULN with no evidence of hemolysis and an alkaline phosphatase value $\leq 2 \times$ ULN or not available;
- For subjects with preexisting ALT **OR** AST **OR** total bilirubin values above the ULN, the following threshold values should be used in the definition mentioned above:
 - For subjects with preexisting AST or ALT baseline values above the normal range: AST or ALT values ≥ 2 times the baseline values and $\geq 3 \times$ ULN, or $\geq 8 \times$ ULN (whichever is smaller).

Concurrent with

- For subjects with preexisting values of total bilirubin above the normal range: Total bilirubin level increased from baseline by an amount of at least $1 \times$ ULN **or** if the value reaches $\geq 3 \times$ ULN (whichever is smaller).

The subject should return to the investigational site and be evaluated as soon as possible, preferably within 48 hours from awareness of the abnormal results. This evaluation should include laboratory tests, detailed history, and physical assessment.

In addition to repeating measurements of AST and ALT, laboratory tests should include albumin, creatine kinase, total bilirubin, direct and indirect bilirubin, gamma-glutamyl transferase, prothrombin time (PT)/international normalized ratio (INR), and alkaline phosphatase. A detailed history, including relevant information, such as review of ethanol, acetaminophen, recreational drug, and supplement consumption, family history, occupational exposure, sexual history, travel history, history of contact with a jaundiced person, surgery, blood transfusion, history of liver or allergic disease, and work exposure, should be collected. Further testing for acute hepatitis A, B, or C infection and liver imaging (eg, biliary tract) may be warranted. All cases confirmed on repeat testing as meeting the laboratory criteria defined above, with no other cause for LFT abnormalities identified at the time, should be considered potential Hy's law cases irrespective of availability of all the results of the investigations performed to determine etiology of the abnormal LFTs. Such potential Hy's law cases should be reported as SAEs.

